3.1.1 Study population and setting

The study population comprises male and female HCWs, aged 18 years or older, working in healthcare facilities (e.g., acute care hospital) or in a community healthcare setting (e.g., clinic) in Indonesia, Kenya, Nigeria, Pakistan, Senegal, South Africa, Uganda, Zimbabwe, and Zambia. Hospitals or healthcare facilities directly participating in the study in target countries of interest should have at least five COVID-19 cases at the time of establishing the registry. Institutions that participate in the study should be able to provide a list of HCWs exposed to COVID-19 patients. As per the WHO definition², HCWs eligible for enrollment are limited, based on the high likelihood of being exposed to COVID-19 patients during patient care, to the following positions:

- Medical doctors*
- Clinical officers*
- Licensed physician assistant or nurse practitioner*
- Registered nurse (or equivalent)*
- Assistant nurse, nurse technician (or equivalent)*
- Phlebotomist
- Clinical pharmacist
- Clinical physical therapist
- Respiratory therapist
- Community healthcare worker

*These should include the following primary specialties:

- Surgery (all sub-specialties)
- Internal medicine (general)
- Pulmonology/critical care
- Emergency medicine

- Geriatrics
- Cardiology
- Infectious disease
- Anesthesiology
- Pediatrics
- Obstetrics/Midwifery
- Other

3.1.1.1 Inclusion criteria

Healthcare workers are eligible for entry into this study only if they meet all the following criteria:

- Healthcare workers aged \geq 18 years.
- Healthcare workers must be exposed through ongoing and recurrent contact to a confirmed or clinically diagnosed COVID-19 patient prior to enrollment, or anticipated within 30 days after enrollment.
- Healthcare workers must consent to provide data for the registry and must be willing to be contacted/reminded about data entry at each follow-up time point.
- Healthcare workers must agree to provide a secondary contact for follow-up.

3.1.1.2 Exclusion criteria

- A confirmed SARS-CoV-2 infection or clinically diagnosed COVID-19 prior to the first known exposure to confirmed or clinically diagnosed COVID-19 patient (Index Date).
- Participation in a ‘blinded’ clinical trial, i.e. unaware of exact treatment received as part of the clinical trial.

Date checks to confirm eligibility criteria will be completed for all subjects. Subsequently, healthcare workers that indicate first exposure to COVID-19 infected patients or COVID-19 symptoms/diagnosis/test results prior to 2020 will be dropped from any analysis. Similarly, healthcare workers that are not exposed to COVID-19 infected patients within 30 days following enrolment will be excluded from any analysis.

3.2 Study period

This registry will remain open and will continue to enroll HCWs until target country level quotas have been reached, or until otherwise determined by the Sponsor.

3.3 Baseline period

Baseline period is defined as timeframe prior to or at index date, i.e. date of the HCW's first known exposure to a confirmed or clinically diagnosed case of COVID-19.

3.4 Follow-up period

The HCWs will be followed up for 12 weeks upon enrollment in the study.

3.5 Study outcomes

3.5.1 Primary Outcome

- Occurrence of SARS-CoV-2 infection among HCWs caring for COVID-19 patients, in terms of time, geography, healthcare setting, and type of HCW. SARS-CoV-2 infection will be defined as a composite outcome diagnosed via the following methods:
 - By test – positive test results – confirmed diagnosis
 - Clinical diagnosis
 - By symptoms
 - Hospitalisation due to COVID-19 illness

Sensitivity analyses will be conducted using confirmed (by positive test results) diagnosis only, and diagnosis by other means, as specified above.

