3.5.2 Secondary Outcomes

For the following outcomes, infection status will be defined as per the composite primary outcome. Ambulatory status and hospitalisation will be based on responses to the relevant questions in the survey. Mortality will be based on the survey response of each subject's secondary contact. Prophylactic treatment will be based on relevant questions from healthcare worker's surveys.

- Occurrence of SARS-CoV-2 uninfected HCWs
- Occurrence of SARS-CoV-2 infection with ambulatory status and no limitation of activities. This will be defined as subjects reporting COVID-19 related symptoms, clinical diagnosis of COVID-19 or positive test results but reporting "No" limitation of activities due to their symptoms and no hospitalisation.
- Occurrence of SARS-CoV-2 infection with ambulatory status and limitation of activities. This will be defined as subjects reporting COVID-19 symptoms, clinical diagnosis of COVID-19 or positive test results and reporting "Yes" to having their usual activities limited being limited due to their symptoms, but no hospitalisation.
- Occurrence of hospitalisation due to COVID-19 illness with mild disease. This is defined as being hospitalised without being admitted to the ICU or without ventilation
- Occurrence of hospitalization due to COVID-19 illness with severe disease. This is defined as being hospitalised with either admittance to the ICU and/or receiving ventilation.
- Occurrence of all-cause mortality

- Type of prophylactic treatments (Chloroquine, Hydroxychloroquine, Azithromycin, Lopinavir/ritonavir, Ivermectin, others) by dose, frequency and duration, overall and by country/region/site. To note, prophylactic treatment use will be defined by relevant indication from 'prophylactic treatment' section of the survey; in addition, if there is an indication of drugs in 'concomitant medications' section that are also listed but not selected under 'prophylactic treatment' section, those indications will be added too.

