3.6.2 Prophylactic treatment (treatment exposure)

- Types, intake frequency, and doses of prophylactic treatments
 - Treatment name: Chloroquine, Hydroxychloroquine, Azithromycin, Lopinavir/ritonavir, Ivermectin, others
 - Date started
 - Date stopped
 - Dose (intake)
 - Duration of treatment
 - Dose frequency and dosing interval
 - Status (stopped/ongoing)
 - Reason for stopping (not available/side effects/expense/other)
 - Number of missed doses and reason (not available/side effects/expense/other)

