3.6.5 Other Covariates

- COVID-19 symptoms (and date the symptoms begin)
 - Fever (temperature over 38°C)
 - Subjective fever (felt feverish)
 - Chills
 - Myalgia (muscles hurt or ache)
 - Rhinorrhea (runny or drippy nose)
 - Pharyngitis (sore throat)
 - Cough (new onset or worsening of chronic cough)
 - Dyspnea (hard to breathe or difficulty breathing)
 - Pneumonia
 - Nausea or vomiting
 - Headache or migraine
 - Abdominal pain (pain in tummy)
 - Asthenia (weakness or loss of strength)
 - Arthralgia (joint pain)
 - Anosmia (loss of smell)

- Ageusia (loss of taste)
- Blue coloring in toes
- Diarrhea (two or more looser-than-normal stools in 24 hours)
- SARS-CoV-2 testing
 - Type of test, if known
 - PCR (positive/negative)
 - Antigen test (positive/negative)
 - Serology (IgG and/or IgM, positive/negative or titer)
 - Date of test
- Household history (COVID-19)
 - Number of household contacts
 - Additional household member(s) exposed to COVID-19 (yes/no). If yes, how many
 - Additional household member(s) with symptoms consistent with COVID-19 (yes/no). If yes, how many?
 - Additional household member(s) diagnosed with COVID-19 (yes/no). If yes, how many
- Healthcare worker-level covariates
 - Demographics at entry
 - Underlying conditions and key comorbidities
 - Job characteristics
 - Concomitant medications
 - Blood type
- Healthcare facility characteristics
 - Country, region
 - Urban or rural setting
 - Type of facility (public/private/community healthcare)
 - Teaching/university hospital or non-teaching
 - Capacity
 - number of patients tested for COVID-19
 - number of COVID-19 patients treated
 - number of hospitalized beds (overall, ICU, emergency department)
 - number of exposed HCWs
 - number of HCWs tested for COVID-19
 - Number of HCWs who developed confirmed or clinically diagnosed COVID-19
 - Number of HCWs who died from COVID-19
 - Approved PPE use policy, and experience of PPE shortage
 - Approved prophylactic treatment policy
 - Shortage of COVID-19 related tests
 - BCG vaccination policy
- Concomitant medications (other than for COVID-19)
 - Antibiotics (yes/no). If yes, please specify.

- Azithromycin
- Trimethoprim/sulphamethoxazole
- Macrolide antibiotics (roxithromycin, clarithromycin, erythromycin)
- Other antibiotics
- Antimalarials (yes/no). If yes, please specify.
 - Hydroxychloroquine
 - Chloroquine
 - Sulfadoxine-pyrimethamine (SP)
 - Other antimalarials
- Antiparasitics (yes/no). If yes, please specify.
 - Ivermectin(yes/no)

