5 Determination of Sample Size

The targeted sample size of approximately 10,000 HCWs assumes that 20% of the study population are non-exposed to potential prophylactic treatments, with a baseline risk of SARS-CoV-2 infection in the study period of 10% (for unexposed: not treated with potential prophylactic treatment). A total of N=10,000 allows for 80% power to identify an effect size of Relative Risk = 0.78.

If these sample sizes are not reached with respect the study population being exposed/non-exposed to potential prophylactic treatments, the relative risk may be detected with lower power or it may not be statistically significant. However, the secondary objectives can still be examined.

6 Statistical analysis

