6.1 Overview

All statistical analyses will be conducted using R (version 1.3.1093), unless otherwise specified.

For all descriptive analyses, categorical variables will be summarized by number of observations and percentage (%). Percentages will be rounded to one decimal place and will be based on available observations (known values), unless otherwise specified. Continuous variables will be summarized using descriptive statistics (n, mean, with standard deviation; minimum, first quartile, median, third quartile,

and maximum). Outliers will be included in descriptions as part of presenting ranges and percentiles (25th and 75th). The mean and SD will be rounded to one decimal place.

All statistical tests will be two-sided and at 5% level of significance.

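### Symptoms alone can make a primary event, the case rule is still open, and complaints that could be side effects of prophylaxis are on the symptom list

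*SAP*

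**What the plan says.** SAP 3.5.1 sets the primary outcome: "SARS-CoV-2 infection will be defined as a composite outcome diagnosed via the following methods". The four routes are a positive test, a clinical diagnosis, symptoms, and hospitalisation for COVID-19. The ambulatory secondary outcomes (SAP 3.5.2, repeated in 6.5) use the same logic and count "subjects reporting COVID-19 related symptoms, clinical diagnosis of COVID-19 or positive test results".

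The symptom list in SAP 3.6.5 runs from fever, cough and loss of smell to non-specific complaints such as "Nausea or vomiting", diarrhoea, abdominal pain, headache and asthenia. Neither document requires a more specific symptom to accompany these.

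The survey allows for side effects. SAP 3.6.2 records "Reason for stopping (not available/side effects/expense/other", with the same options for missed doses. Protocol section 10 says that adverse events are not collected, and Protocol 8.8.1 says that submitted data are not queried.

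SAP 6.3.9 says that the descriptive symptom tables will help decide which symptoms, or groups of them, count as infection. Those tables are not split by prophylaxis use. The same descriptive stage (SAP 6.3) compares weekly incidence by prophylaxis use.

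SAP 3.5.1 and 6.7 plan sensitivity analyses on each component alone: test, symptoms, clinical diagnosis, hospitalisation.

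**The concern.** A complaint caused by the drug adds events among users that have no counterpart among non-users. If such a complaint can qualify as infection, the outcome is misclassified differently in the two groups, and the primary hazard ratio moves toward harm. A protective drug could look inert, and an inert drug could look harmful. A larger sample does not reduce this bias.

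The same complaints also arise from other causes in both groups. Counted as infections, they dilute the hazard ratio toward 1. The two effects can act together.

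The data offer no direct way to separate them afterwards. There is no adverse event record, and the side-effect option on the form says why a drug was stopped or a dose missed but not which complaint was involved. The case definition therefore has to deal with the problem, and it is not yet fixed. The registry aims to inform policy on prophylactic use, so an error in either direction matters.

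**Working it through.** **Inputs.** SAP section 5: "The targeted sample size of approximately 10,000 HCWs assumes that 20% of the study population are non-exposed to potential prophylactic treatments", so 2,000 unexposed and 8,000 exposed; "baseline risk of SARS-CoV-2 infection in the study period of 10" percent in the unexposed; and "A total of N=10,000 allows for 80% power to identify an effect size of Relative Risk = 0.78". The design risk in users is therefore 0.78 × 10% = 7.8%. SAP 6.1: "All statistical tests will be two-sided and at 5% level of significance".

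**The plan's own figure.** Expected events are 2,000 × 0.10 + 8,000 × 0.078 = 824. Schoenfeld's formula with HR 0.78 and 20% unexposed gives 81.4% power, close to the stated 80%. A pooled two-proportion test gives 87.7%. The two-proportion form is used below because it handles changed risks directly; it approximates the planned Cox frailty model.

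**Power formula.** With unexposed risk c, exposed risk t and pooled risk p, power = Φ[(|t − c| − 1.96·SE0)/SE1], where SE0 = √[p(1 − p)(1/2,000 + 1/8,000)] and SE1 = √[c(1 − c)/2,000 + t(1 − t)/8,000].

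**Assumption.** A share s of users has an excess complaint that is counted as infection, independently of true infection. The documents give no value for s, so a range is shown.

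**A drug with the design effect.** Observed user risk = 0.078 + 0.922s. Setting this equal to 0.10 gives the break-even: s = 0.022/0.922 = 2.39%.

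| s | user risk | observed RR | power to show benefit |
|---|---|---|---|
| 0 | 7.80% | 0.78 | 87.7% |
| 0.5% | 8.26% | 0.83 | 68.9% |
| 1% | 8.72% | 0.87 | 43.4% |
| 2% | 9.64% | 0.96 | 7.1% |
| 2.39% | 10.00% | 1.00 | – |
| 5% | 12.41% | 1.24 | – (85.9% chance of significant harm) |

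**An inert drug, no background complaints.** User risk = 0.10 + 0.90s. At s = 1% it is 10.9% (RR 1.09). Then p = 0.1072, SE0 = 0.00773, SE1 = 0.00756, and (0.009 − 0.01516)/0.00756 = −0.81, so the chance of significant harm is 21%. At s = 2% the user risk is 11.8% (RR 1.18) and the chance is 62%.

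**Adding a shared background b of qualifying complaints in both groups** (assumed 5–30%). Unexposed risk c = 0.10 + 0.90b. With the design effect and s = 0, user risk is 0.078 + 0.922b.

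- Break-even: the difference is 0.022(1 − b) and the remaining at-risk share is 0.922(1 − b), so the ratio is still 2.39%.
- Dilution at s = 0: for b = 5%, RR = 12.41/14.5 = 0.86 and power falls to 70%. For b = 30%, RR = 35.46/37.0 = 0.96 and power falls to 25%.
- Inert drug, with user risk c + (1 − c)s:

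| b | false harm, s = 1% | false harm, s = 2% |
|---|---|---|
| 0 | 21% | 62% |
| 5% | 15% | 46% |
| 10% | 12% | 36% |
| 20% | 9% | 24% |
| 30% | 8% | 18% |

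The 30% entry at s = 1% is 7.5% before rounding. Background complaints therefore lower the chance of a false harm finding, but they also erode the ability to show a real benefit.

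**The case against.** The strongest reply is that every number above needs a case rule that the SAP does not contain. SAP 6.3.9 leaves open which symptoms or groups qualify, and the eventual rule could exclude isolated gastrointestinal complaints or headache. This stands, and it makes the finding conditional. It does not settle the matter: nothing obliges the rule to exclude them, and a rule based only on the number of symptoms could still admit two gastrointestinal complaints reported together.

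Second, sensitivity analyses exist. A reader might infer that nothing in the plan checks for this problem; SAP 3.5.1 and 6.7 show otherwise. A gap between the symptoms-only and test-only hazard ratios would be a warning. But each planned analysis isolates one component, and none is the composite with symptom-only events removed. No tests are mandated (SAP 3.1), and test shortage is a recorded facility variable, so the test-only analysis may be sparse.

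Third, a reader might infer that these complaints arise only in treated workers. They do not. They have other causes, and non-users may take other antibiotics, antimalarials, antiretrovirals or NSAIDs that the SAP does not recode as prophylaxis. Only the excess among users biases the comparison, and s is defined as that excess.

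Fourth, SAP 6.4.1 starts the clock for treated workers 7 days after initiation. This may place early side effects before time zero, but the SAP does not say how such events are handled, and follow-up runs for 12 weeks with continuing use possible. The effect of the shift is unknown.

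**Conclusion.** The point holds conditionally. The symptom route is in the primary composite, non-specific complaints are on the list, no adverse event data exist to separate drug effects, and the case rule is not pre-specified. If the rule admits these complaints, an excess among users pushes the primary hazard ratio toward harm, while shared background complaints pull it toward 1.

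The size rests on the SAP's design figures, on independence of the excess from true infection, and on assumed values of s and b. The 2.39% is a tipping point. A reader might take it as an expected bias, but the documents give neither the type nor the rate of side effects and do not support that reading. Likewise, 21% and 62% are the false-harm chances with no background complaints; with the assumed 5–30% background they are about 8–15% and 18–46%.

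**What to change.** 1. In SAP 6.7, add the primary analysis with symptom-only events removed, so that an event is a positive test, a clinical diagnosis or a hospitalisation.
2. Tabulate symptom-only events by symptom group and by on/off prophylaxis at the time of the report.
3. In SAP 3.5.1 and 6.3.9, fix the symptom case rule before any comparison by prophylaxis use, including the incidence comparison in SAP 6.3. State that gastrointestinal complaints, headache or asthenia alone do not make a symptom-only event. Which symptoms do qualify is for the sponsor and the Scientific Advisory Committee to decide.

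The cost is SAP wording, one further model run and one table, all on data already collected. The added analysis will have fewer events, and some true untested infections with only non-specific symptoms will not be counted.

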3.5.2 Secondary Outcomes

For the following outcomes, infection status will be defined as per the composite primary outcome. Ambulatory status and hospitalisation will be based on responses to the relevant questions in the survey. Mortality will be based on the survey response of each subject's secondary contact. Prophylactic treatment will be based on relevant questions from healthcare worker's surveys.

- Occurrence of SARS-CoV-2 uninfected HCWs
- Occurrence of SARS-CoV-2 infection with ambulatory status and no limitation of activities. This will be defined as subjects reporting COVID-19 related symptoms, clinical diagnosis of COVID-19 or positive test results but reporting "No" limitation of activities due to their symptoms and no hospitalisation.
- Occurrence of SARS-CoV-2 infection with ambulatory status and limitation of activities. This will be defined as subjects reporting COVID-19 symptoms, clinical diagnosis of COVID-19 or positive test results and reporting "Yes" to having their usual activities limited being limited due to their symptoms, but no hospitalisation.
- Occurrence of hospitalisation due to COVID-19 illness with mild disease. This is defined as being hospitalised without being admitted to the ICU or without ventilation
- Occurrence of hospitalization due to COVID-19 illness with severe disease. This is defined as being hospitalised with either admittance to the ICU and/or receiving ventilation.
- Occurrence of all-cause mortality

- Type of prophylactic treatments (Chloroquine, Hydroxychloroquine, Azithromycin, Lopinavir/ritonavir, Ivermectin, others) by dose, frequency and duration, overall and by country/region/site. To note, prophylactic treatment use will be defined by relevant indication from 'prophylactic treatment' section of the survey; in addition, if there is an indication of drugs in 'concomitant medications' section that are also listed but not selected under 'prophylactic treatment' section, those indications will be added too.

3.6 Other study variables

All of the following variables are collected at baseline and for each week of follow-up up to 12 weeks.

3.6.1 Clinical Outcomes Variables

- WHO Ordinal Scale for Clinical Improvement of COVID-19 (adapted, abbreviated version)
 - SARS-CoV-2 (uninfected/infected)
 - Ambulatory status (limitation/no limitation of activities)
 - Hospitalized with no intensive care unit (ICU) or mechanical ventilation (mild)
 - Hospitalized with ICU and/or mechanical ventilation (severe)
 - Death

3.6.2 Prophylactic treatment (treatment exposure)

- Types, intake frequency, and doses of prophylactic treatments
 - Treatment name: Chloroquine, Hydroxychloroquine, Azithromycin, Lopinavir/ritonavir, Ivermectin, others
 - Date started
 - Date stopped
 - Dose (intake)
 - Duration of treatment
 - Dose frequency and dosing interval
 - Status (stopped/ongoing)
 - Reason for stopping (not available/side effects/expense/other)
 - Number of missed doses and reason (not available/side effects/expense/other)

3.6.3 History of exposure to COVID-19 patients

- At enrollment
 - Self-reported ongoing and recurrent exposure (yes/no)
 - WHO exposure definition (3 questions) (yes/no)
 - Direct patient care (yes/no)
 - Face-to-face contact (yes/no)
 - Present during aerosol-generating procedure (yes/no)

- Weekly follow-up
 - Self-reported ongoing and recurrent exposure (yes/no)
 - WHO exposure definition (3 questions) for past week
 - Days worked past week
 - Number of COVID-19 cases exposed to in the past week

3.6.4 Personal Protective Equipment Use

- At enrollment
 - Type and use of PPE (yes always, yes not always, no) prior to enrollment
- Weekly follow-up
 - Type and use of PPE (yes always, yes not always, no) at time of confirmed exposure(s) in the past week
 - Number of COVID-19 exposures in the absence of a mask
 - Longest COVID-19 exposure in the absence of a mask

Details on the following types of PPE will be captured:

- Mask (type of mask—N95 respirator mask, other)
- Eye protection/goggles/face shield
- Gown
- Gloves

3.6.5 Other Covariates

- COVID-19 symptoms (and date the symptoms begin)
 - Fever (temperature over 38°C)
 - Subjective fever (felt feverish)
 - Chills
 - Myalgia (muscles hurt or ache)
 - Rhinorrhea (runny or drippy nose)
 - Pharyngitis (sore throat)
 - Cough (new onset or worsening of chronic cough)
 - Dyspnea (hard to breathe or difficulty breathing)
 - Pneumonia
 - Nausea or vomiting
 - Headache or migraine
 - Abdominal pain (pain in tummy)
 - Asthenia (weakness or loss of strength)
 - Arthralgia (joint pain)
 - Anosmia (loss of smell)

- Ageusia (loss of taste)
- Blue coloring in toes
- Diarrhea (two or more looser-than-normal stools in 24 hours)
- SARS-CoV-2 testing
 - Type of test, if known
 - PCR (positive/negative)
 - Antigen test (positive/negative)
 - Serology (IgG and/or IgM, positive/negative or titer)
 - Date of test
- Household history (COVID-19)
 - Number of household contacts
 - Additional household member(s) exposed to COVID-19 (yes/no). If yes, how many
 - Additional household member(s) with symptoms consistent with COVID-19 (yes/no). If yes, how many?
 - Additional household member(s) diagnosed with COVID-19 (yes/no). If yes, how many
- Healthcare worker-level covariates
 - Demographics at entry
 - Underlying conditions and key comorbidities
 - Job characteristics
 - Concomitant medications
 - Blood type
- Healthcare facility characteristics
 - Country, region
 - Urban or rural setting
 - Type of facility (public/private/community healthcare)
 - Teaching/university hospital or non-teaching
 - Capacity
 - number of patients tested for COVID-19
 - number of COVID-19 patients treated
 - number of hospitalized beds (overall, ICU, emergency department)
 - number of exposed HCWs
 - number of HCWs tested for COVID-19
 - Number of HCWs who developed confirmed or clinically diagnosed COVID-19
 - Number of HCWs who died from COVID-19
 - Approved PPE use policy, and experience of PPE shortage
 - Approved prophylactic treatment policy
 - Shortage of COVID-19 related tests
 - BCG vaccination policy
- Concomitant medications (other than for COVID-19)
 - Antibiotics (yes/no). If yes, please specify.

- Azithromycin
- Trimethoprim/sulphamethoxazole
- Macrolide antibiotics (roxithromycin, clarithromycin, erythromycin)
- Other antibiotics
- Antimalarials (yes/no). If yes, please specify.
 - Hydroxychloroquine
 - Chloroquine
 - Sulfadoxine-pyrimethamine (SP)
 - Other antimalarials
- Antiparasitics (yes/no). If yes, please specify.
 - Ivermectin(yes/no)
 - Other antiparasitics
- Antiretrovirals for Human Immunodeficiency Virus (HIV) (yes/no). If yes, please specify.
 - Lopinavir
 - Ritonavir
 - Tenofovir
 - Nelfinavir
 - Other antiretrovirals
- Antivirals (yes/no). If yes, please specify.
 - Oseltamivir
 - Favipiravir
 - Arbidol
 - Anti-hepatitis C treatments
 - Remdesivir
 - Other antivirals
- Medication for high blood pressure and cardiovascular disease (yes/no). If yes, please specify.
 - Angiotensin-converting enzyme (ACE) inhibitor (e.g. lisinopril, enalapril)
 - Angiotensin II receptor blockers (ARB) inhibitor (e.g. losartan, irbersartan)
 - Other anti-hypertensive for high blood pressure
 - Other medicine for high blood pressure and cardiovascular disease (E.g. antiarrhythmics, inotropes, chronotropes)
- Nonsteroidal Anti-inflammatory Drugs (NSAIDs) E.g. Aspirin, Ibuprofen, Indomethacin, Celecoxib, Diclofenac (yes/no).
- Botanicals-- Artemisia teas (COVID Organics) (yes/no)
- Immunocompromising drugs such as corticosteroids, cancer chemotherapy, cyclosporine, colchicine, drugs for autoimmune conditions such as lupus, rheumatoid arthritis or Crohn's disease (yes/no)
- Changes in concomitant medications

Any prophylactic medications that are indicated as concomitant medications being taken by HCWs will be considered during analysis as part of a prophylactic treatment. This will apply to the following prophylactic medications:

- Hydroxychloroquine
- Chloroquine
- Azithromycin
- Lopinavir/ritonavir
- Ivermectin

4 Data security/privacy

- The Application has received a full penetration test from an accredited third party to cover cyber security threats.
- Data is segregated between the collection nodes and analysis nodes. Only information technology support staff have access to the data in the nodes for the express purposes of server support.
- All data on the analysis platform is tokenized with a unique patient token generated on the node. This tokenization uses a powerful salted hash algorithm (a document explaining this process may be reviewed if necessary but cannot be released for security reasons).
- Access to the data platform is controlled by Azure Active Directory accounts managed by the Parexel Support team.
- Access to the Application can only be achieved by end user registration using a set of industry leading authentication providers.
- The application has a unidirectional data flow from the node to the analysis platform so there is no risk of horizontal escalation issues.

5 Determination of Sample Size

The targeted sample size of approximately 10,000 HCWs assumes that 20% of the study population are non-exposed to potential prophylactic treatments, with a baseline risk of SARS-CoV-2 infection in the study period of 10% (for unexposed: not treated with potential prophylactic treatment). A total of N=10,000 allows for 80% power to identify an effect size of Relative Risk = 0.78.

If these sample sizes are not reached with respect the study population being exposed/non-exposed to potential prophylactic treatments, the relative risk may be detected with lower power or it may not be statistically significant. However, the secondary objectives can still be examined.

6 Statistical analysis

